Despite significant improvement in preterm infant survival, the incidence of bronchopulmonary dysplasia (BPD) in infants born ≤ 28 weeks gestational age (GA) has been relatively stable at $\sim 40\%$ ^{i,ii,iii}, with 10,000–15,000 new cases estimated annually^{iv}. Delivery room (DR) management of preterm infants during the initial resuscitation has a significant impact on future development of BPD. Current DR practice as recommended by the Neonatal Resuscitation Program (NRP), focuses on providing positive pressure ventilation (PPV) for intubated infants based on pressure limited ventilation (PLV). But with rapidly changing pulmonary compliance during the early newborn period, PLV may lead to under or over inflation of the lungs and induce significant volutrauma, barotrauma and/or atelactetrauma, all of which are associated in the pathogenesis of BPD. No studies have specifically reported tidal volume (TV) provided in the DR in intubated infants with current PLV practices. Similarly, no study has evaluated the safety and efficacy of volume targeted ventilation (VTV) in the DR and its impact on BPD.

With the proposed study, in Phase I, we aim to demonstrate that measuring TV in intubated infants receiving PPV via PLV is feasible. We also seek to demonstrate that with PLV, TV is highly variable in the first few hours of life, even with the same peak inspiratory pressures (PiP) due to rapidly changing pulmonary compliance. A successful Phase I will demonstrate that measuring TV is feasible in the DR, and with information on real time actual TV achieved during PPV, it is possible to target the TV for a goal TV by adjusting the PiP provided.

Phase II will be a pilot randomized control trial to demonstrate feasibility of VTV compared to PLV. We will also aim to understand the pulmonary mechanics and physiology during VTV. A successful Phase II will demonstrate VTV is feasible, is associated with stable TV, decreased peak inspiratory pressure and oxygen needs compared to PLV, and not associated with increased complications compared to PLV. It will thereby justify a larger randomized control trial with enough power to evaluate the efficacy of VTV in reducing BPD and other long term pulmonary morbidities for preterm infants.

[figure not shown]
BACKGROUND

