PHASE I: No specific withdrawal/termination criteria will be required as this is an observational study to assess feasibility of measuring tidal volume in the DR. Infant will continue to receive routine care as recommended by NRP, even if TV measurements are unsuccessful.

PHASE II: Control Arm: No specific withdrawal/termination criteria will be required, as these infant will continue to receive routine care per NRP recommendations without any study related intervention.

Intervention Arm: If TV cannot be measured or VTV cannot be provided within 60 seconds of initiating PPV via the ETT, the infant will be automatically switched to receiving routine care as recommended by the NRP.

INFORMED CONSENT PROCESS AND TIMING

Who: Parent.

When: "Deferred consent" is being requested after the birth of the child. The study process starts as soon as the baby is born and requires intubation as determined by the clinical team providing resuscitation. We will obtain a deferred consent from the parents only if the baby requires intubation in the delivery room and the TV measurements were obtained. We will approach the parents to use the data that was collected in the delivery room.

Rationale for deferred consent: *In an ideal situation, the consent should be obtained prior to study intervention. However, since the study intervention starts within few seconds to minutes of the baby's birth and it is not*

possible to determine which baby will need intubation in the delivery room, it would be unrealistic to have the opportunity to obtain informed consent we will aim for "deferred consent" process. As this study only present minimal risk to the infants and the device being used is an FDA approved device for use in neonates, a deferred consent is being requested for from the IRB.

How much time to decide: Since study related interventions has already occurred and we are asking parents to give consent for using this information as well as review of electronic medical records parents will have adequate time to make this decision free of any coercion to participate in the study.

Person authorized to obtaining consent: All investigators, program coordinator associated with the study.

SUBJECT FEES: None

REIMBURSEMENT/RENUMERATION FOR PARTICIPTION: None

RISK BENEFIT ASSESSMENT

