Providing VTV to the VLBW infants is a standard of care practice upon admission to the NICU, with this study we seek to provide more physiologic VTV to the infant immediately after birth without any delay.

Phase I: No risk and no benefit directly to the patient, as this is the observational phase of the study. Information obtained from this phase study may potentially be beneficial by supporting the need for future studies in preterm infants with need for invasive respiratory support.

Phase II: Infants in intervention arm will receive the same routine care with additional information about the TV being delivered to the study infants. The provider's ability to adjust the PiP to provide goal TV may be potentially beneficial for the study infants, as in current DR practice the delivered tidal volume is unknown and infant may be receiving TV out of the set goal range. Infants in the control arm will not have any direct risk or benefit. The only concern would be adding less than 1ml of dead space with the flow sensor, which may or may not be of any clinical significance at all.

UNANTICIPATED PROBLEMS AND SERIOUS ADVERSE EVENT REPORTING

Unanticipated problems and serious adverse events to the subjects related to the study will be reported to the IRB within 48 hours of the occurrence.

RANDOMIZATION

Phase I: No randomization. All infants will receive pressure regulated breaths, 40-60 breaths/min, PiP of 20-24cm of H₂O as recommended by 2017 Neonatal Resuscitation Program (NRP) guidelines. Providers will be blinded from the measured TV during the resuscitation.

Phase II: All infants born <32 weeks will be randomized to one of the study group. Randomization will be via sealed envelope, opened in DR after the decision to intubate is made, with a 1:1 randomization ratio. To keep the gestational age in the two study arm relatively similar, as we are proposing only a small sample size for this current study, randomization will be stratified by gestation age group (Randomization subgroup I: <28 weeks and subgroup II: 28-32 weeks). Infants in both the arms will have a flow sensor at the ETT connected to Respironics NM3 monitor (Philips Healthcare, Eindhoven, Netherlands), to measure breath to breath TV.

INTERVENTION

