Control Arm: Infant will receive pressure regulated breaths, 40-60 breaths/min, PiP of 20-24cm of H₂O as recommended by 2017 Neonatal Resuscitation Program (NRP) guidelines. Reading of the TV will be blinded from the providers as in routine clinical situations

Intervention Arm: Infants in the intervention arm will receive VTV following intubation. Peak inspiratory pressure (PiP) provided via T-piece resuscitator will be visible to the providers, and the provider can regulate the PiP to achieve the desired TV goal (4-6 ml/kg), at a rate of 40-60 breaths/min according to a predefined protocol

The infants will continue to receive respiratory support as assigned by the study arm for the first 48 hours of life, following which they will receive routine VTV and weaning as per standard of care NICU practice.

BLINDING

Phase I: Providers will be blinded from the measured TV during the resuscitation.

Phase II: Due to the providers being aware of ventilation process and the need for change in ventilator settings based on the infant's TV, blood gas, blinding the providers will not be possible. Acknowledging this, we will be blinding the outcome assessment. The individual collecting the data for the two groups and performing the physiologic BPD testing will be blinded on the infant's randomization status. Need for discharge home on oxygen will be assessed by a physician not associated with the study and strict guidelines will be followed for discharge home on oxygen. Provider performing long term outcome assessment will also be blinded from the infant randomization status during the study.

PRIMARY OUTCOME VARIABLE

Phase I: Successful measurement of tidal volume in within 60 seconds of intubation and initiation of PPV.

Phase II: Timing of initiation of VTV will be similar to PLV.

STUDY ENDPOINTS

The study patient will continue in the randomized arm for the first 48 hours of life with ongoing data collection for the first 48 hours after initial neonatal resuscitation. After the first 48 hours, infant will continue standard of care per the NICU providers, with continued data collection for longer term outcomes.

SAMPLE SIZE

Phase I: We will select a convenience sample of 10 successive patients for the initial phase of the study.

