Phase II: We will enroll a total of 30 patients (15 per study group). The sample size was selected to insure sufficient number of patients to estimate variability and effect sizes^{xxi} and to estimate recruitment rates. For example, with 30 patients, the width of the 95% confidence will be about 55% as wide as the standard deviation. This estimate will help develop sample size estimates for future studies.

DATA COLLECTION AND STORAGE

Study data will be collected and managed using a secure, web-based, password protected RedCap (Research Electronic Data Capture) data base^{xxii}. Baseline demographic maternal and infant characteristics, TV, PiP, mean airway pressure, PEEP, FiO₂, resuscitation details, duration of invasive mechanical ventilation, duration of non-invasive respiratory support (non-invasive mechanical ventilation, continuous positive airway pressure), duration of oxygen treatment, home O₂ requirement, BPD incidence and severity along with pulmonary complications will be collected. Standard BPD definition of mild (oxygen use for 28 days), moderate (oxygen need at 36 weeks), or severe (ventilatory support at 36 weeks), along with physiologic BPD testing at 36 weeks will be used to define BPD. This data will also be used prospectively in a future randomized control trial if feasibility study is successful. The research team members and DSMB will have access to the full data set.

DATA ANALYSIS

As the study is designed as a pilot, no formal tests of hypotheses will be conducted^{xxiii}. In Phase I, our goal is to attain skill and competency with using the device, as well as to establish that our measures are reliable and valid. Descriptive statistics will be use to assess the feasibility of measuring TV in the DR. Feasible will be defined as being able to successfully measure the TV in 80% of the infants within 60 seconds of starting PPV via the endotracheal tube.

For Phase II of the pilot project, data analysis will be limited to point estimates (e.g., means and proportions). We will describe the feasibility of using VTV in the DR, and data analysis will be limited to estimating the point estimates (e.g., means and proportions) and variability of ventilatory measures in each group and overall. We will also estimate recruitment and attrition rates, as well as the duration of the consenting process.

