We will use the pilot phase to begin identifying and assessing the frequency of adverse events for developing safety measures. Additionally, the pilot data will be used to estimate effect sizes and variability so that sample size and statistical power may be computed for a later randomized control trial.

Although this study will not be powered to evaluate differences in longer term pulmonary outcomes like BPD, we will still assess for possible trends in difference of BPD and other pulmonary outcomes between the two groups. Being a feasibility study, this study will not be powered to evaluate the safety and other long term outcomes between the two arms, but we will collect and analyze the safety data especially since we will be using the enrolled patient data for the future randomized control trial.

VULNERABLE POPULATION

This study involves studying newborn infants, who are considered vulnerable population. In phase I, the subjects involved in the study will have minimal risks as they will receive standard of care practices and we will only assess our ability to measure the TV in this population. In Phase II, the control arm has minimal risk as they will receive standard of care practices. The intervention arm may potentially have direct benefit as with the information about TV during resuscitation, we can target our PiP for goal TV, thereby minimizing volutrauma and/or atelectotrauma. Thus, overall this study poses none to minimal risk for the study subjects and may potentially benefit the infants in the intervention arm.

For the Phase II the study related interventions will be done only after a written informed parental consent has been obtained.

DATA AND SAFETY MONITORING

Safety data will be monitored closely for all enrolled subjects with special focus on infants randomized to the intervention arm in Phase II. Subjects in the intervention arm, based on the tidal volume generated, the maximum PiP will be limited at 30cm of H₂O, as it would be considered unconventional to require more PiP than 30cm of water in the immediate neonatal phase for longer than 60 seconds duration. If the tidal volume cannot be measure within 60 second, the patients will continue to receive conventional PLV during the time eliminating any potential harm to the patient. We will monitor for development of any pulmonary complication in the enrolled subjects including but not limited to pneumothorax, pneumo-mediastinum, and pulmonary interstitial emphysema.

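### The one precision figure for 30 infants names no parameter and does not describe an arm difference, which 15 per arm fixes only to about ±0.75 SD; Phase II plans no confidence intervals

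*Combined protocol and SAP*

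**What the plan says.** All references are to the combined protocol and SAP.

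- **Sample Size, Phase II.** Thirty infants, 15 per group, are said to be enough to estimate variability, effect sizes and recruitment rates. The one supporting figure, offered as an example, is that "with 30 patients, the width of the 95% confidence will be about 55% as wide as the standard deviation". The sentence does not say what the interval is for.
- **Data Analysis, Phase II.** The plan states that "data analysis will be limited to point estimates (e.g., means and proportions") and adds the "variability of ventilatory measures in each group and overall". No Phase II confidence interval is mentioned, and no hypothesis tests are planned.
- **Primary Outcome Variable, Phase II.** "Timing of initiation of VTV will be similar to PLV". This is a statement about two arms.
- **Data Analysis, on later use.** "the pilot data will be used to estimate effect sizes and variability so that sample size and statistical power may be computed" for a subsequent randomised trial. The Statement of Purpose describes that trial as "a larger randomized control trial with enough power to evaluate the efficacy of VTV in reducing BPD".
- **Withdrawal/Termination Criteria, Phase II intervention arm.** "If TV cannot be measured or VTV cannot be provided within 60 seconds of initiating PPV via the ETT", the infant is moved to routine care.
- **Randomization.** "randomization will be stratified by gestation age group" (below 28 weeks, and 28 to 32 weeks).

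**The concern.** The sample size is justified for two purposes, variability and effect sizes, by one number that can serve only one of them. A reader who sees 55% of an SD beside a promise to estimate effect sizes may take it as the precision of the arm comparison. The true interval for that comparison is much wider.

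The analysis section then removes the safeguard that would show this. With point estimates alone, the report will give two means or two proportions and no indication of how far apart the arms could really be. That matters in two places. The primary outcome asks whether timing is alike in the two arms, and two bare estimates from 15 infants each cannot show how large a difference remains compatible with the data. The pilot effect is also to enter the sample-size calculation of the next trial, where its uncertainty would be hidden.

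**Working it through.** **Inputs.** 30 infants, 15 per arm, 1:1 allocation, 95% confidence, stated width about 0.55 SD (Sample Size; Randomization). No attrition rate is assumed in the plan. The calculations for means and SDs take approximate normality, equal SDs in the arms and no attrition.

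**1. Reproducing the 55%.** The 95% interval for an SD runs from s·√(df/χ²₀.₉₇₅) to s·√(df/χ²₀.₀₂₅).

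| SD estimated from | df | Lower | Upper | Width |
|---|---|---|---|---|
| all 30 infants | 29 | √(29/45.72) = 0.796 s | √(29/16.05) = 1.344 s | 0.548 s |
| both arms, pooled within arm | 28 | √(28/44.46) = 0.794 s | √(28/15.31) = 1.352 s | 0.559 s |
| one arm | 14 | √(14/26.12) = 0.732 s | √(14/5.63) = 1.577 s | 0.845 s |

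The first row gives the plan's figure, and the second is nearly as close.

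**2. Other candidates for the 55%.**
- One mean, n = 30: full width 2 × 2.045/√30 = 0.747 SD. No match.
- One-arm mean, n = 15: half-width 2.145/√15 = 0.554 SD. This matches numerically, but it is a half-width (full width 1.108 SD) and uses 15 infants, whereas the text speaks of a width with 30.
- Difference in means, 15 per arm: see step 3. No match as a half-width or a full width.

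The SD reading is therefore the best match, though the text does not prove it. Neither matching reading is a between-arm quantity.

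**3. Precision of an arm difference in a continuous measure.** Half-width = t₀.₉₇₅,₂₈ × √(1/15 + 1/15) = 2.048 × √(2/15) = 2.048 × 0.365 = 0.748 SD, so the full width is 1.496 SD. That is 1.496/0.548 = 2.7 times the quoted width. As an illustration, an observed difference of 0.5 SD would have an interval of about −0.25 to +1.25 SD.

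**4. Precision for a binary outcome.** The introduction gives a BPD rate of about 40% for infants of 28 weeks or less. Taking 6/15 in each arm as an illustration:
- One arm, exact (Clopper–Pearson): 16% to 68%.
- Arm difference, Newcombe: the Wilson limits for 6/15 are 0.198 and 0.643, so the half-width is √[(0.400 − 0.198)² + (0.643 − 0.400)²] = 0.315. The difference is 0 ± 32 percentage points.

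**5. The timing outcome.** Steps 1 to 3 do not carry over to it. An infant in the intervention arm who has not received VTV within 60 seconds of starting PPV is switched to routine care and may have no VTV start time. If a mean were taken only over infants who reached VTV, and the clock started at PPV, it could not exceed 60 seconds whatever the number of failures. A quantity that avoids this is the proportion with VTV started within 60 seconds, out of all infants randomised to VTV. At 12/15 (illustrative) its exact 95% interval is 52% to 96%.

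**The case against.** The strongest reply is that this is a pilot doing what a pilot should. The 55% sentence is an example, the text after it says the estimate will help size future studies, and learning an SD for that purpose is sound. The plan disclaims hypothesis tests and says it is not powered for BPD or safety. Intervals could be added at reporting from the same data.

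Much of this stands. The 55% is not an arithmetic error, and nothing here asks for tests, power or a larger pilot. It does not close the gap, though. Intervals are estimation, not testing, and the plan itself justifies its sample size by a confidence width. The disclaimers on power cover long-term and safety outcomes, not the primary timing outcome or the use of pilot effect sizes. The text also limits the analysis to point estimates, so intervals cannot be taken as implied.

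Three stronger readings are tempting, and the documents do not support them.
- *That ±0.75 SD measures the uncertainty in the timing outcome.* It assumes fully observed, roughly normal values, and VTV times may be cut off at 60 seconds.
- *That the timing comparison is biased as planned.* The plan does not say that only infants who reached VTV will be averaged, and the Phase II objectives under Specific Aim 1 separately count infants who fail VTV and are switched. The risk is conditional: it arises because the handling of these infants is not stated.
- *That the later trial would inherit ±0.75 SD.* That trial is aimed at BPD, a binary outcome, so the illustration of ±32 percentage points is the relevant one.

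**Conclusion.** The concern holds as an incomplete precision statement and an analysis plan that omits intervals. The 55% is correct for an SD from all 30 infants and should be kept for that purpose. It gives no support to the effect-size purpose, and it overstates the precision of per-arm variability: about 85% of the SD for one arm, against 55% overall. A between-arm difference in a continuous, fully observed measure is known only to about ±0.75 SD. For a binary outcome near 40%, the difference is known to about ±32 percentage points.

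The continuous figures rest on normality, equal SDs and no attrition; losses would widen them. The binary figures rest on illustrative counts. That the parameter is unnamed, that 55% does not describe an arm difference, and that no Phase II interval is planned are all firm. This should be changed, but it does not stop the pilot from going ahead.

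**What to change.** 1. **Sample Size.** Name the parameter behind the 55%. If it is the overall or pooled SD, say that the 95% interval width is about 55–56% of the SD. Add that it is about 85% for a single-arm SD, and that an arm difference in means is known to about ±0.75 SD.
2. **Data Analysis.** Replace the limit to point estimates with estimates plus 95% confidence intervals: exact for single proportions, and intervals for arm differences. For continuous measures, adjust the difference for the gestational-age stratum used in randomisation. With balanced strata that explain no variance this costs almost nothing (±0.749 SD at 27 df, against ±0.748 SD).
3. **Timing outcome.** Analyse all randomised infants in their assigned arm. Report the proportion with VTV started within 60 seconds with an exact interval, and state how infants switched at 60 seconds are handled. Do not average only over those who reached VTV. This concerns the analysis only, not the switching rule.
4. **Planning the later trial.** Use the pilot mainly for the SD, recruitment and attrition. Do not size the trial on the pilot's point-estimate effect without its interval.

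The cost is rewording and slight extra analysis, with no extra infants. The stated precision will look less favourable, and the later trial's target difference will need its own justification.

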Low intubation rates in the DR and low enrollment rate: With the increased usage of noninvasive respiratory support, the number of intubated infants in the DR might be lower than anticipated. In that situation, we are open to making this study a multicenter feasibility study with University of Massachusetts Medical School-Worcester as a potential partner. Additionally, for Phase I, we can also evaluate the feasibility of measuring TV in infants undergoing “INSURE” (intubation, surfactant and rapid extubation) for respiratory distress syndrome, as these infants also tend to be premature <32 weeks infants with rapidly changing pulmonary compliance after administration of surfactant therapy.

ANTICIPATED RESULTS AND IMPACT

Phase I: Tidal volume can be rapidly measured in more than 80% of intubated infants in the DR. TV is highly variable in the immediate newborn period, which can result in significant over or underdistension of the lungs, predisposing the infant to lung injury from volutrauma and/or atelectotrauma. A successful Phase I study will demonstrate the potential that a goal TV can be targeted during PPV by adjusting the PiP provided.

Phase II: We anticipate demonstrating that delivering VTV in DR is feasible for optimal lung recruitment; which when continued in the NICU may potentially reduce lung injury as well as long-term pulmonary complications including BPD. The study will provide evidence and pilot data to support the need for a larger, multi-center randomized control trial comparing VTV versus PLV during DR neonatal resuscitation. It will also provide evidence supporting the lung protective impact of VTV, and can potentially lead to significant change in practices from pressure limited to volume targeted respiratory support during neonatal resuscitation.

PUBLICATION PLANS

The results from the study will presented in various local, regional and national conferences, with the eventual goal of publishing the results in a peer review journal.

REFERENCES

ⁱ Zysman-Colman Z., Tremblay G.M., Bandeali S., Landry J.S. Bronchopulmonary dysplasia—trends over three decades. *Pediatr. Child Health.* 2013;18:86–90

ⁱⁱ Day C.L., Ryan R.M. Bronchopulmonary dysplasia: Old becomes new again! *Pediatr. Res.* 2016 doi: 10.1038/pr.2016.201.

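### The later RCT is to be sized on effect sizes estimated from 15 infants per arm, which the pilot cannot estimate closely enough for that use

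*Combined protocol and SAP*

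**What the plan says.** **Size and purpose.** Sample Size, Phase II: "We will enroll a total of 30 patients (15 per study group"). The number was chosen "to insure sufficient number of patients to estimate variability and effect sizes", and also to estimate recruitment. The only precision statement is that "with 30 patients, the width of the 95% confidence will be about 55% as wide as the standard deviation"; the parameter is not named.

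**Use of the results.** Data Analysis: "the pilot data will be used to estimate effect sizes and variability so that sample size and statistical power may be computed" for a later RCT. No outcome is attached to this sentence. The Statement of Purpose says that the later trial should have "enough power to evaluate the efficacy of VTV in reducing BPD" and other long-term pulmonary morbidities.

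**Analysis.** Data Analysis rules out formal hypothesis tests and limits Phase II to point estimates, with the variability of ventilatory measures. It says that the study is not powered for BPD, safety or long-term outcomes, but adds that "we will still assess for possible trends in difference of BPD and other pulmonary outcomes between the two groups".

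**Impact.** Anticipated Results and Impact, Phase II: "It will also provide evidence supporting the lung protective impact of VTV, and can potentially lead to significant change in practices".

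**The concern.** Using a small pilot's observed effect as the planning effect of the next trial is a known weakness. The estimate is very noisy, and a trial that follows an encouraging result tends to be planned on an effect that is too large, and so enrols too few patients. Here the next trial would enrol very preterm infants and might be unable to answer its question.

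The plan contains nothing to limit this. It names no minimum important difference, no outside source for the effect and no confidence interval for a between-arm difference. The quoted 55% may reassure a reader that effect sizes will be well estimated. A BPD trend reported without an interval, beside a sentence anticipating evidence of lung protection, invites over-reading.

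**Working it through.** **Inputs from the protocol.** 15 per arm, "with a 1:1 randomization ratio" (Sample Size; Randomization). BPD about 40% in infants of 28 weeks or less (Specific Aims and Hypothesis). The rate for intubated infants under 32 weeks is not given.

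**Assumptions.** Control BPD 40%; true rate with volume targeted ventilation (VTV) 30%, 25%, 20% or 15%; later RCT at two-sided 5% and 80% power; no dropout.

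**1. The plan's 55%.** The 95% CI for an SD runs from SD × √(df/χ²₀.₉₇₅) to SD × √(df/χ²₀.₀₂₅). With n = 30 and df = 29:
- lower limit √(29/45.72) = 0.796 SD
- upper limit √(29/16.05) = 1.344 SD
- width 0.548 SD, which matches the stated 55%.

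The CI for a mean does not match: 2 × 2.045/√30 = 0.747 SD. So the figure is the precision of an SD in all 30 infants.

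**2. Precision of an effect.**
- Difference in means, df = 28: width 2 × 2.048 × √(2/15) = 1.50 SD. This is 1.50/0.548 = 2.7 times the quoted width.
- Difference in BPD, 40% in both arms: half-width 1.96 × √(2 × 0.4 × 0.6/15) = 0.351, about 35 points.
- Exact binomial enumeration with 40% in both arms: VTV shows fewer BPD cases in 43% of pilots, and at least two fewer in 29%. Direction alone therefore says little.

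**3. One example.** Pooled-variance formula, per arm: n = [1.960√(2p̄(1−p̄)) + 0.842√(p₁(1−p₁)+p₂(1−p₂))]²/(p₁−p₂)².
- True 40% v 30%: (1.322 + 0.565)²/0.01, giving 356 per arm.
- Pilot shows 6/15 v 3/15, that is 40% v 20%: (1.270 + 0.532)²/0.04, giving 82 per arm.
- Power of 82 per arm if the truth is 40% v 30%: Φ[(0.10 − 1.960 × 0.0745)/0.0741] = Φ(−0.62) = 27%.

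**4. All pilots.** I enumerated the 16 × 16 possible pairs of BPD counts. For each pair favouring VTV, the RCT was sized for 80% power on the observed rates, and its power was then computed at the true rates.

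| True BPD, control v VTV | n per arm needed | Pilot favours VTV | Of these, true power <80% | Of these, true power <50% |
|---|---|---|---|---|
| 40% v 30% | 356 | 65% | 77% | 61% |
| 40% v 25% | 152 | 76% | 64% | 46% |
| 40% v 20% | 82 | 85% | 57% | 36% |
| 40% v 15% | 49 | 92% | 58% | 27% |

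**5. Sensitivity.**
- If any non-zero difference were used whatever its sign, the RCT would fall below 80% power in 49% to 63% of all pilots across these four rows.
- Control rates of 30%, 50% and 60% gave 61% to 78% below 80% power after a favourable pilot, for true reductions of 10 to 25 points.
- For a continuous outcome sized on a favourable pilot effect, the share is 71% at a true standardised effect of 0.2, 55% at 0.5 and 49% at 1.0.

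**The case against.** **The sizing outcome is not named.** A reader might infer that the protocol commits to using the observed BPD difference as the planning effect. It does not. The sizing sentence names no outcome, the planned variability estimates are for ventilatory measures, and the BPD sentence is a separate paragraph that opens with a disclaimer. The BPD link comes from reading Data Analysis with the Statement of Purpose. This stands, and the BPD figures are conditional on it. The rule that pilot effect sizes will feed the sample size is explicit, and the 1.50 SD width applies to any continuous outcome.

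**There is no BPD go/no-go.** A reader might also infer that a BPD trend decides whether the RCT proceeds, so that a true benefit could be abandoned on noise. The Statement of Purpose defines success by feasibility, stable tidal volume, lower pressure and oxygen needs, and no increase in complications. BPD is not among them, and no trend rule is stated.

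**The results depend on assumed effects.** True power below 50% is the majority result only at 40% v 30% among the four cases. If the control rate is fixed at 40% and only the difference is taken from the pilot, 61% becomes 54%, and the share below 80% power at 40% v 20% is about one half. This too stands.

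**The protocol is candid.** It plans no formal tests and disclaims power for BPD. The impact sentence is hedged about practice change and concerns the study as a whole, not the BPD comparison alone. That softens the wording point but does not repair the sizing plan.

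**Conclusion.** The concern holds in a limited form. The plan would use effect sizes from 15 infants per arm to compute the later RCT's sample size and power, and the pilot cannot support that. The precision it quotes belongs to an SD; a between-arm difference in means is about 2.7 times less precise, and a BPD difference is known only to about ±35 points.

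If the observed BPD difference became the planning effect after a favourable pilot, the RCT would be below 80% true power in 57% to 77% of cases, and below 50% in 27% to 61%. These ranges rest on a 40% control rate borrowed from infants of 28 weeks or less, true VTV rates of 15% to 30%, and an 80% power target.

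The documents do not support saying that the RCT will be sized on BPD, or that most such trials would have less than 50% power whatever the true effect. The pilot's own procedures and primary outcome are unaffected. This should be corrected before the pilot results are used for planning.

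**What to change.** **Sample Size and Data Analysis.** State that the later RCT will be sized on a pre-specified, clinically important difference in its primary outcome, and not on the pilot's observed effect. Take the control event rate from the unit's wider cohort of intubated infants under 32 weeks, where available. State that the 55% figure refers to the SD.

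**Keep what the pilot can supply.** Retain as planning inputs, each with a 95% CI, the SDs of ventilatory measures and the rates of recruitment, consent, attrition, measurement failure and switching from VTV to pressure limited ventilation. The SDs are a legitimate pilot product, so the pilot need not be confined to feasibility rates. They are still imprecise: the CI for one arm's SD is 0.84 SD wide.

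**BPD.** Report counts by arm with a 95% CI for the difference, and drop the trend statement.

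**Anticipated Results and Impact.** Limit the lung-protection and practice-change sentence to feasibility and ventilatory measures.

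**Cost.** Protocol wording only, with no extra infants, visits or data. The pilot's stated impact becomes more modest.
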